6.9 Criteria for Removal from Study

Criteria for removal from the study are described in this section:

- Participant is unable to tolerate the study intervention
- Participant is unable to complete all required study procedures
- New information shows that the study intervention is no longer in participants best interest
- The site investigator no longer feels this is the best option for participant
- The Sponsor decides to stop the study
- The research ethics board (REB) withdraws permission for this study to continue

6.10 Analytic Plan

Baseline characteristics and management data will be presented as means (continuous measures) or proportions (categorical or ordinal data) with 95% confidence intervals or interquartile ranges (IQR). An independent Methods Center statistician, external to the study team, will conduct all analyses by the intention-to-treat principle.

Primary Outcome: Our primary outcome is poor neurologic outcome at 1 year and will be presented in terms of relative risk with 95% confidence intervals. We define poor neurologic outcome as mRS ≥ 4 . As a secondary analysis, we will report absolute risk reduction using a proportional odds approach which is more sensitive for detecting a shift over the entire spectrum of outcome (mRS 7-point ordinal scale), and thus increases the statistical power.^{48,67,68} We will also conduct adjusted analyses for age, sex, SAH severity (using WFNS grade), clip vs coil and DCI using the generalized linear model.

Secondary Outcomes: Our secondary outcomes (see 5.6) will be assessed using multivariable linear or logistic regression models for continuous and dichotomous outcomes respectively. We will adjust for the same characteristics as in the primary outcome.

6.11 Proposed frequency of analyses

We plan one full interim, blinded analysis after the first 370 patients randomized to be reviewed by the Data Safety Monitoring Board (DSMB) guided by a pre-specified charter. Regular (biannual) reports of patient recruitment and adverse event reporting will be provided to the DSMB.

6.12 Planned subgroup analyses

A priori subgroup analyses include patient age, sex and those with associated intraventricular hemorrhage and DCI at time of enrolment.

7 Safety Reporting

7.1 Adverse Event Monitoring and Source Documentation

All recipients are to be assessed for adverse events according to local institutional practice, except where additional assessment is required per protocol. Source documentation of reportable adverse events should be according to institutional practice, except in cases where additional information is required to be documented by the protocol.

7.2 Adverse Event Reporting

7.2.1 Expected Serious Adverse Events (eSAE)

Have been defined a priori and are being collected and reported as study outcomes and as such will not be labeled nor reported a second time as serious adverse events.⁶⁸

7.2.2 Unexpected Serious Adverse Events (uSAE)

All uSAEs are to be brought to the attention of the site PI (following site specific standard operating procedures). Causality (see section 7.3.4) of the uSAE should be adjudicated by the site PI. All possibly or related uSAEs are to be reported in the Data Collection Forms (both study arms) as described in this section:

- A. Monitoring and reporting should begin on the first day of study intervention and continue until either:
 - a. the uSAE has been resolved
 - b. day 28 (post-ictal bleed), death or discharge whichever occurs first
 - i. if the uSAE remains ongoing at day 28 it will be reported as such
- B. Supporting source documentation of all reported uSAEs must be submitted for additional and final central adjudication.
- C. Abnormal laboratory results do not need to be recorded unless considered by the investigator to be relevant in terms of subject or trial safety (or in relation to a serious adverse event that is being reported).

7.2.3 Serious Adverse Event Reporting

All reportable unexpected SAEs (see 7.2.2 and definition section 7.3.3) must be reported to the Coordinating Center **within 72 hours** of the site's knowledge of the unexpected SAE. The Study Chair and/or Study Steering Committee will review all unexpected SAE's received from the sites. If an unexpected SAE is confirmed, a document summarizing the SAE will be distributed to participating sites. Sites should follow the guidelines of their local REB with respect to the submission of SAEs that occur at the site as well as SAE Notifications

7.3 Definitions

7.3.1 Adverse Event (AE)

The International Conference on Harmonization (ICH) definition of an adverse event is: Any untoward medical occurrence in a patient or clinical investigation subject administered a pharmaceutical product and which does not necessarily have a causal relationship with this treatment. An adverse event (AE) can therefore be any unfavorable and unintended sign (including an abnormal laboratory finding, for example), symptom, or disease temporally associated with the use of a medicinal (investigational) product, whether or not related to the medicinal (investigational) product.

7.3.2 Serious Adverse Event (SAE)

In reference to the ICH and Health Canada definition of a Serious Adverse Event, we will define as any untoward medical occurrence that either:

- Results in death
- Is life-threatening
- Requires prolongation of existing hospitalization
- Results in persistent or significant disability/incapacity, or
- Results in a congenital anomaly/birth defect.

7.3.3 Unexpected Adverse Event (uAE)

In accordance with the ICH Guidelines: An unexpected adverse event is one in which the nature or severity is not consistent with the applicable product information; in this instance, the red blood cell transfusion trigger protocol. For example, death from transfusion would be an unexpected serious adverse event as opposed to death from sepsis.

A subset of uAE's will meet SAE criteria (section 7.3.2), this subset, being both unexpected and serious, will be reported as uSAE's as described in section 7.2.3.

7.3.4 Causality

Investigators are required to assess the relationship, if any, of each AE (that meets the criteria for reporting) to the red cell transfusion(s) trigger strategy. Clinical judgment is to be used to determine the degree of certainty with which an AE can be attributed to the intervention. Causality criteria are defined as follows:

- **Not related:** There is not a reasonable possibility that the adverse event may have been caused by the study intervention.
- **Possibly related:** The AE may have been caused by the study intervention; however there is insufficient information to determine the likelihood of this possibility
- **Related:** There is a reasonable possibility that the AE may have been caused by the study intervention.

8 Trial Management

8.1 Participant enrolment, consent, randomization and allocation concealment

Local research coordinators will screen each patient admitted for aSAH to either the Intensive Care Unit or Intermediate Care Unit for up to 10 days after the qualifying bleed (Figure 1B). Enrolment up to 10 days is necessary as previous work has demonstrated that the negative effect on outcome was most pronounced in patients with anemia between days 6 and 11³⁶. Further, our SAHaRA observational study demonstrated that 87% of incident anemia occurred within the first 10 days, and that 97% did so while admitted to a high-acuity unit.²⁸ The risk of new onset DCI, a significant threat to morbidity and mortality in this population occurs most frequently within 7-10 days but its duration may surpass this period.¹⁸ In our pilot RCT, the median day of randomization was 3 days (IQR 2-5 days).

As in our pilot RCT, patients meeting eligibility criteria (or their substitute decision maker (SDM) in the event the patient is unable to provide informed consent) will be approached for informed consent, using a mixed consent model and in accordance with Good Clinical Practice as well as standard local procedures as approved by each local REB. As in the pilot RCT, we will use a deferred informed consent approach due to the time-sensitive nature of the intervention whose potential benefit lies in timely administration. Substitute decision makers are not always immediately available, or the timeliness of the approach may be inappropriate, such that it may be impractical to explain the study, obtain informed consent and initiate the intervention in a timely manner.

The same web based randomization system maintained at the Coordinating Center will be used to allocate treatment assignments. Under the guidance of the site principal investigator (SI) or research coordinator (RC), the participant's eligibility criteria will again be confirmed with a checklist using a web interface.

Upon meeting the randomization criteria, patients will be randomized in a 1:1 manner to either restrictive or liberal RBC transfusion strategy groups. A schedule of the random treatment allocations, stratified by center will be prepared by an independent biostatistician at the Coordinating Center. All investigative team members will remain blinded to the allocation schedules.

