9.2 Protecting against sources of bias

Allocation of patients is concealed to prevent selection and information bias. Given the nature of the intervention (RBC transfusion strategy) and its effect on serum hemoglobin measurements, an open-label design is necessary as it is not possible to blind treating practitioners after randomization. As such, we have incorporated independent central blinded outcome assessment and adjudication for all clinical outcomes. Misclassification bias is minimized by applying strict diagnostic criteria for aSAH in the eligibility criteria. Performance bias will be minimized by stratifying patients according to participating sites to ensure equal randomization across sites. We will also track eligible but non-enrolled patients to describe reasons for non-enrolment according to a taxonomy of reasons listed on a study data form. Further, we have attempted to minimize subjectivity in all of the outcome measures by centralizing and blinding the outcome assessor to the treatment allocation and utilizing validated tools for morbidity measures (mRS, FIM and EQ5D) (see Section 6.6). To further reduce risk of bias (performance, attrition, detection and reporting), for the primary outcome, a validated interview/questionnaire administered over the telephone, electronically or by mail will be performed by the assessor (trained and qualified study personnel) blinded to the intervention and who has had no part in the management of the patients.

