3.3 Analysis populations

Intention to Treat population: this population includes all aSAH patients randomized except those who were a post-randomization exclusion, withdrew consent, or were lost to follow up.

Per Protocol Population: this population is the intention to treat population except those who had a protocol violation (as defined in 3.2).

The primary analysis of all outcomes will be conducted on the Intention to Treat population. A secondary, sensitivity analysis, on the Per Protocol population will also be conducted and reported separately, accompanied by a description of the population characteristics, in the supplement.

Section 4 – Trial Population

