4.2 Withdrawal/Follow-up

When a patient is lost to follow-up their 12-month mRS score will be missing, therefore, this patient cannot be included in the analysis of the primary outcome. Whenever possible, these patients will be included in the secondary outcome analyses.

No data will be analysed for patients who withdraw consent, but such patients will be listed in the CONSORT diagram.

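### SAP 3.3 and 4.2 drop all data from patients who withdraw consent, some of whom may first be asked after open-label allocation, and nothing checks the effect on the in-hospital outcomes

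*Protocol*

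**What the plan says.** Protocol 8.1 describes recruitment "using a mixed consent model and in accordance with Good Clinical Practice" and adds: "As in the pilot RCT, we will use a deferred informed consent approach due to the time-sensitive nature of the intervention". The reason given is that a decision maker may not be at hand, or the moment may be wrong, so that "it may be impractical to explain the study, obtain informed consent and initiate the intervention in a timely manner". Protocol 9.2 says that "an open-label design is necessary as it is not possible to blind treating practitioners after randomization".

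Protocol 6.10 says an independent statistician "will conduct all analyses by the intention-to-treat principle". It lists no exclusions. SAP 3.3 defines the Intention to Treat population differently: "this population includes all aSAH patients randomized except those who were a post-randomization exclusion, withdrew consent, or were lost to follow up". That set is used for the primary analysis of every outcome. SAP 4.2 is stricter still on withdrawals: "No data will be analysed for patients who withdraw consent, but such patients will be listed in the CONSORT diagram". Patients lost to follow-up are treated more generously in the same section, which keeps them in the secondary analyses where possible.

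SAP 5.2 brings withdrawals back in one place, the best-case/worst-case sensitivity analysis of the primary outcome. SAP 2.6 lists in-hospital death, DCI, radiographic vasospasm and new infarction as secondary outcomes, and adverse events to 28 days as tertiary. None of these has a comparable analysis.

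**The concern.** Where consent is deferred, the patient or decision maker may first decide about the trial when the arm is known and the early course is visible. Refusal can then be related to both arm and prognosis. A rule that deletes all data on refusal turns this into selection after randomization.

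The in-hospital outcomes are the most exposed. A death, infarct or transfusion reaction may already be on the case report form when consent is refused, and the rule removes it. These are the trial's mortality and harm comparisons, and a reader would take them as intention-to-treat estimates because the SAP gives the set that name.

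**Working it through.** **The plan's own figure.** For 40% vs 30%, two-sided 5%, 80% power and no continuity correction, 356 per arm are needed, or 712 in total. Allowing 3% loss, 712/0.97 = 734.02, rounded up to 735, close to the stated 740. Power is 81.5% with 370 per arm and 80.3% with 359 per arm. Loss of numbers is therefore not the issue; selective loss is.

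**Formula.** If an arm has true risk p, a fraction l refuses and is deleted, and a share r of refusers has the event, the observed risk is (p − l·r)/(1 − l).

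**In-hospital death, no true effect.** The documents give none of the inputs. Assumed: p = 20% in both arms, r = 50%, refusal 5% in the liberal arm and 1% in the restrictive arm.

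- Liberal: (0.20 − 0.05 × 0.5)/0.95 = 0.175/0.95 = 18.4%.
- Restrictive: (0.20 − 0.01 × 0.5)/0.99 = 0.195/0.99 = 19.7%.
- Risk ratio (RR), liberal to restrictive: 0.935.
- Refusal 3% vs 1%: liberal 0.185/0.97 = 19.1%, RR 0.97.
- Rates swapped (1% liberal, 5% restrictive): RR 1/0.935 = 1.07.
- Refusal unrelated to death (r = 20%): liberal (0.20 − 0.01)/0.95 = 20.0%, RR 1.00.

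**What retention and bounds would do in the 5% vs 1% case.** If the refusers' deaths were recorded before refusal and kept, the liberal risk is 0.175 + 0.025 = 20%, the restrictive risk 0.195 + 0.005 = 20%, and the RR is 1.00. If nothing is kept, the bounds are 0.175/(0.195 + 0.01) = 0.85 and (0.175 + 0.05)/0.195 = 1.15. Bounds alone are wide; recorded data remove the problem where their use is allowed.

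**Primary outcome.** With the plan's 40% in both arms, refusal 5% vs 1% and 60% to 80% of refusers having a poor outcome (assumed):

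- At 60%: 0.370/0.95 = 38.9% vs 0.394/0.99 = 39.8%, a spurious 0.9 points.
- At 80%: 0.360/0.95 = 37.9% vs 0.392/0.99 = 39.6%, a spurious 1.7 points.
- Type I error is about 5.6% to 7.5% (normal approximation, 370 × (1 − l) × 0.97 analysed per arm).

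SAP 5.2 exposes this risk. With 30% vs 40% observed and 11 missing per arm (3%), the RR is 0.75 (95% CI 0.61 to 0.92), best case 0.70 (0.57 to 0.85), worst case 0.83 (0.68 to 1.005). These use unadjusted risk ratios, not the SAP's mixed model.

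**Two gaps in that protection.** First, 5.2 imputes even where the outcome is known: a recorded death in the liberal arm becomes favourable in the best case, and one in the restrictive arm becomes favourable in the worst case. Second, 5.2 leaves out patients randomized in error, and 3.3 has an undefined category of post-randomization exclusions. No section says whether refused deferred consent is a withdrawal or such an exclusion. If it is put with the exclusions, refusers may fall outside the bounds too.

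**The case against.** The strongest case against is one of scope. A reader might infer that every patient is consented after treatment. The documents do not support that: the model is mixed, the share deferred is not given, and Protocol Table 4 lists informed consent at baseline. A reader might also infer that the primary risk ratio is left unprotected. It is not, because SAP 5.2 bounds it and names withdrawals. Nor do the documents show that any bias occurred or that it favours the liberal arm. Exclusion criterion 3 already removes known objectors to transfusion, and the restrictive arm may also be transfused. All of this stands.

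SAP 4.2 may also simply apply ethics terms. Protocol 8.1 defers to local board approval, and the consent pages are not available here, so how many refusers' data could lawfully be kept is unknown. That limits the remedy but does not justify a blanket rule for everyone.

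Two tempting repairs fail. The public-record search in Protocol 9.4 is for patients who cannot be reached, not for those who refused. Adding only known deaths to the complete-case primary analysis makes inclusion depend on outcome. With uninformative refusal of 5% vs 1%, 40% poor outcome and 20% in-hospital death, the observed risks become (0.95 × 0.40 + 0.05 × 0.20)/(0.95 + 0.01) = 0.390/0.960 = 40.6% and (0.99 × 0.40 + 0.01 × 0.20)/(0.99 + 0.002) = 0.398/0.992 = 40.1%. That is a spurious 0.5 points of harm where the present plan has none.

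The in-hospital outcomes are reported without p-values (SAP 3.1). That lowers the stakes, but the estimates and intervals will still be read.

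**Conclusion.** The concern holds in a limited form. As written, the SAP can discard recorded in-hospital deaths, DCI, vasospasm, infarctions and adverse events for patients who refuse after allocation is known. It does so within a set labelled intention to treat and provides no check for those outcomes. The primary outcome is bounded, subject to the unresolved conflict between 4.2 and 5.2 and the missing classification of deferred refusals.

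This is an unguarded risk, not demonstrated bias. Under the assumed rates the in-hospital death RR moves from 1.00 to between 0.935 and 0.97, or by a similar amount the other way if refusal is higher in the restrictive arm. It does not move if refusal is unrelated to outcome. The result rests on refusal rates, a death rate and a death share among refusers that the documents do not give. It should be corrected before database lock, which is when SAP 2.5 places publication of the SAP.

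**What to change.** Amend SAP 3.3, 4.2 and 5.2 as follows.

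- State that refusal of deferred consent is handled as withdrawal, and define post-randomization exclusion separately.
- Keep data recorded up to withdrawal in the in-hospital and safety analyses unless the patient, the decision maker or the ethics terms forbid it.
- Extend the best-case/worst-case bounds to the in-hospital outcomes for withdrawals whose outcome is unknown.
- In the primary-outcome bounds, score a known death as mRS 6 in both scenarios where use of the data is permitted. Do not add only known deaths to the main complete-case analysis.
- Reconcile the blanket rule in 4.2 with the inclusion of withdrawals in 5.2.
- Report refusals by arm and timing, beyond the CONSORT listing already planned.
- Call the set modified intention to treat if exclusions remain.

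The cost is SAP wording, a few extra sensitivity analyses and a check of each board's approved consent terms. No new patients or contacts are needed. The downside is that patients whose terms forbid use of their data stay excluded, and their number is unknown.

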8.2 Baseline Characteristics and Co-Interventions

The study team will capture important baseline characteristics (e.g. age, sex, ethnicity, language, comorbidities, aneurysm and SAH characteristics/grade) at time of enrolment for comparison between the 2 study groups. In this pragmatic trial, patient management outside of RBC transfusion will be left to the discretion of the treating team and in accordance with practice guidelines¹⁸ which will be made available to all participating centers and clinicians. Potentially confounding cointerventions (e.g.: nimodipine use, aneurysm securing technique, blood pressure and DCI management) will be carefully documented daily in the case report form by the site research coordinators.

8.3 Study Centers

From the pilot RCT, 5 centers have already committed to the trial with REB approval and executed contracts. We have demonstrated the ability to enroll into the trial with a mean randomization rate of > 1 patient/center/month recruiting. Eight additional centers have agreed to participate in the full trial including Kingston General Hospital (Kingston), Royal Alexandra Hospital (Edmonton), Centre Hospitalier de l'Université de Montréal (Montréal), Centre Hospitalier Universitaire de Sherbrooke (Sherbrooke), London Health Sciences Center, Sunnybrook Health Sciences Center, Toronto Western Hospital, and Manitoba Health Sciences Center (Winnipeg) (see supporting letters). Future additional centers for the full trial have been identified through our CCTG partners and will be onboarded as required to meet the proposed recruitment timelines of this study, some of these centers may be international.

8.4 Day to day management of the trial

The trial will be coordinated from the Ottawa Hospital Research Institute (OHRI – Study sponsor). The Trial Coordinator will be responsible for the day-to-day proceedings of the trial including collecting, validating and collating reported data from study sites and liaising with the statistician. The trial statistician will be based out of the Methods Center of the OHRI. The RCs of the participating sites will carry out patient screening, recruitment, consent, case report filing, data collection, storage and dissemination to the coordinating center. Site co-investigators will act as leadership, educators, recruiters and resources for the day-to-day proceedings and financing. We have established policies and procedures including an electronic web-based randomization and case-report form as utilized in the pilot RCT.

9 Potential Challenges and mitigation strategies

9.1 Study recruitment and compliance

Recruitment Strategies: Prior to Trial Start-up: We will hold a start-up meeting with the participating sites in conjunction with a Canadian Critical Care Trials Group Scientific Meeting. Education sessions at the participating sites for physicians (neurologists, neurosurgeons, neuroradiologists and intensivists), resident staff and bedside nurses will take place in the form of rounds, mini-sessions and morning teaching to inform on the need for this study, study rationale and participant inclusion criteria. During the Trial: Logs of screened patients including details of ineligibility and logs of participant refusals (either by treating physician, patient or substitute decision maker) will be sent monthly to the coordinating center for analysis and to review strategies to increase enrolment. Quarterly updates on recruitment efforts will be disseminated to all participating centers along with recruitment reminders.

Recruitment Rate: The SAHaRA pilot RCT has demonstrated the ability to successfully recruit patients into this trial applying the same eligibility criteria. With a goal of >1patient/center/month, we have demonstrated feasibility in recruiting. Like the 5 pilot sites, the proposed trial centers are all tertiary care centers with active neurovascular programs. Once all centers are actively enrolling, we anticipate a recruitment duration of 3 years to meet the pre-specified sample size.

Study Compliance: Study compliance will be measured in 2 domains:

1) **Adherence to allocated transfusion threshold:** This will have occurred if: 1) a RBC transfusion is given in response to the transfusion threshold being crossed; or 2) a repeated hemoglobin value no longer crosses the threshold ending the transfusion threshold event. **Non-adherence** will be considered to have occurred if a) an RBC transfusion occurs before a transfusion threshold is crossed; or b) in the liberal arm, a transfusion is not given following a threshold crossing. Non-adherence will be considered a *deviation* if: 1) the early transfusion occurs within 5 g/L above the allocated threshold (e.g. ≤ 105 g/L for the liberal arm or ≤ 85 g/L for the restrictive arm) or, 2) in the liberal arm, an RBC transfusion does not occur for a hemoglobin measure up to 5 g/L below the threshold (i.e.: a transfusion does not occur for a Hb of 95-100 g/L). All other threshold event non-adherences will be considered a protocol violation. Details on non-adherence (date and hemoglobin level prior to transfusion) and reasons for non-adherence will be recorded. In the Pilot RCT we had 93% compliance with RBC transfusion according to allocation at the mid-point interim analysis. In the event of an active blood loss associated with hemodynamic instability, as defined by the treating team, standard resuscitation practices

prevail (including blood product administration). Transfusion under this circumstance would not be a protocol violation. The allocated transfusion strategy will resume when hemodynamic stability is achieved and it is the opinion of the treating team that active bleeding has stopped. Transfusion outside of hemoglobin thresholds for symptomatic anemia will be recorded, but not considered a protocol violation.

2) Adherence to transfusion protocol (timely transfusion): As in the pilot, we endeavor not to exceed 6 hours from transfusion threshold event to transfusion initiation, in keeping with revascularization time performance measures in stroke literature^{70,71}. Transfusion protocol adherence is thus defined as an RBC transfusion initiated within 6 hours of threshold crossing, or Randomization. Non-adherence will be considered to have occurred if there is a delay of more than six hours between transfusion threshold event and transfusion initiation. Transfusions occurring more than 6 hours but within 24 hours will be considered a protocol deviation. A violation is a transfusion initiated greater than 24 hours from the threshold event. We will document reasons for non-adherence in the study case report form.

To improve protocol compliance and awareness we have involved neurosurgeons, interventionalists, transfusion medicine and intensivists at each study site. We will provide on-call house staff and clinicians end-of-the-day and start-of-the-weekend reminders about the study, both for future recruitable patients and enrolled patients. Reminders in the form of stickers and flagged pages will mark enrolled patients' medical record. A list of randomized patients will be kept in the transfusion medicine lab to allow for a secondary check of protocol adherence for when RBC transfusion is ordered. We will monitor daily hemoglobin measures to ensure compliance of transfusion within 6-hour target of meeting the threshold.

